1. TITLE

NCT03881553: Interventions to help children recover in the hospital.

2. EXTERNAL IRB REVIEW HISTORY*

N/A

3. PRIOR APPROVALS:

Conflict of Interest (COI):

The PI ([name]) is a co-inventor on a patent for the stochastic vibratory stimulation (SVS) mattress device, which will be used in this project. There is an approved mitigation plan in place at UMass due to a potential financial conflict of interest.

COI Mitigation Approval Letter uploaded on eirb.

Clinical Engineering Department:

Medical and research devices with power sources will be inspected for safety, including grounding and minimal current leakage as necessary, prior to being placed in service and will be inspected annually by the Clinical Engineering Department. The Clinical Engineering Department Electrical Safety Inspection protocol shall be used as the inspection procedure. All measurements shall meet the NFPA 99, IEC 60601 healthcare standards for electrical safety. All medical devices with power sources regardless of ownership shall be inspected for safety, including grounding and minimal current leakage as necessary, prior to being placed in service.

Upon receiving new equipment with power sources for use in the study, a study investigator will notify the Clinical Engineering Department at [contact] directly, or through the Materials Management Department, regardless of the purchase rental, loan, lease, evaluation, or demonstration arrangement. The outside manufacturers/ contractors are responsible for the quality and performance of all rented, leased, contracted, or equipment on evaluation.

Biohazardous Agents:

- N/A

Radiation:

- N/A

4. PROCEDURES INVOLVED

Randomization: Subjects will participate in up to four study sessions that include NEATCap intervention and/or SVS mattress intervention based on duration of subject's hospitalization, availability of research personnel, availability of device and fit-ability of the device around the head and ears of the subject (currently we have 4 sizes, but additional sizes may become available during the study period). Subject will serve as his/her own control, and will receive alternating periods of intervention ON vs intervention OFF.

NCT03881553 Study Protocol and Statistical Analysis Plan

- **Devices: Purpose of use and regulatory approval status (see also section 32).** The two experimental devices used in this study are Abbreviated IDEs:
 - 1) **NEATCap Device:** The NEATCap (“Dreamies”) device is an experimental device engineered by NEATCap, LLC (patent pending). It is a circumaural passive noise protection device comprised of a soft fabric headband with a specially-designed ear covering that simulates the acoustic filtering of a pregnant mother’s body. The device was designed to dampen unsafe, high frequency noises (e.g., alarms from medical equipment) while allowing passage of low frequency sounds such as a caregiver’s voice. There are no electrical components to this device. The device is a circumaural hearing protector, FDA product code EWE [510(K) exempt device], which as per FDA rulings does not require IDE to test before the device is marketed;
see:
<http://www.accessdata.fda.gov/scripts/cdrh/cfdocs/cfPCD/classification.cfm?ID=EWE>. The predicate device for NEATCap “Dreamies” is MiniMuffs Neonatal Noise Attenuators, marketed by Natus Medical since 1995 that has been used on NICU infants in high-noise situations for many years. Indications for use state “The device is intended for use on newborns to provide reduction in the sound level reaching the newborn’s ears.” The proposed studies in this docket involves non-invasive measurements with NEATCap device, also an EWE circumferential hearing protector device, for up to four session periods, not to exceed 24 hours in any one period.
 - 2) **SVS Mattress Device:** The SVS mattress device is an experimental device. It will be used to gently stimulate the subject. The specially-constructed mattresses are similar to the usual hospital mattress except that inside the mattress foam there is a device that vibrates the foam, controlled by an external unit. The mattresses are constructed by Cofab Design, LLC or other contracted company using patent specifications, modified to adjust for various size cribs and beds. The device components in the mattress and external control unit may be modified with improved technologies to allow for testing of various displacements and mattress sizes, and to help ensure consistency of mattress integrity over time. The mattresses are designed so that the foam vibrates throughout the entire mattress. We are aware of no deleterious effects of the SVS mattress. We have studied over 100 premature infants (since 2001) and over 50 infants exposed to opioids *in utero* (since 2010) using the SVS mattress without incident or apparent side effects. The FDA has not approved the SVS mattress as a treatment for prematurity or withdrawal. Sound level produced by the mattress will be monitored and will not exceed 75 decibels (60-70 dB is normal conversation; 75 dB is about the sound of an average car interior on a highway). The UMass/Memorial Health Care Biomedical Engineering will certify the electrical safety of the mattress devices.
- **Research procedures:** Subjects will participate in up to four sessions, applying either the NEATCap and/or SVS mattress. Sessions will last on average between 8 and 12 hours, and will not exceed 24 hours in any one session. All sessions will

NCT03881553 Study Protocol and Statistical Analysis Plan

be performed at the subject's NICU/CCN or PICU/PIU bedside. Infants and children enrolled in this study will receive routine, standard of care, which may include pharmacological management as prescribed by their primary medical caregiver complementary to the intervention (NEATCap; SVS mattress). Nurses are instructed to provide routine care and to intervene as they would typically do despite the presence of an investigator by the bedside.

Standard measurements and recordings. Physiologic recordings with and without electroencephalographic (EEG) activity will be obtained through state-of-art acquisition system (e.g., Embla, Nihonkohden or other) obtained (hardcopy) or recorded (digital) directly from hospital monitor (e.g., Philips, ixTrend or other). Respiratory inductance plethysmography (RIP) will be used to measure breathing. Respiratory belts will be placed around the chest wall and/or abdomen to record respiratory muscle movements, and allow for detection of inter-breath intervals (IBI) of respiration. Sensors over the skin surface of the torso will be used to record electrocardiographic activity (ECG), and allow for detection of R-R intervals of the ECG signal (index of inter-beat heart rate). Electrodes over the head and face area will be used to measure EEG activity at the surface of the cortex to allow for sleep stage classification using EEG signal analysis; electrode impedance will be measured to help ensure data quality. A probe attached to the foot or wrist will measure arterial-blood oxygen concentration; quality of the plethysmographic activity characterized in the pulse signal will allow for identification of movement periods. Movement periods will be assessed further via actigraphy with a wireless sensor worn around the infant's leg and/or arm that records limb movement. Skin temperature will be measured continuously with a sensor placed under the armpit or back. A sound and light meter placed near the head will record sound frequency and intensity, and changes in light level. Overt behavioral data will be recorded using a camera with a wide-angled lens placed within or near the subject's bed. Medical history (including toxicology screens) and demographic data will be obtained on the infant/child and on the biological mother by manual medical record review or electronically extracted via UMCCTS Data Lake.

Data acquisition, recording and archival. Physiological data will be digitally recorded (~50-1kHz samples per channel) using bedside data acquisition system or recorded directly from hospital bedside monitor onto secure research computer/laptop. Acquisition systems enable fully synchronized recordings of physiological signals, audiometry, photometry and digital video images. Comments regarding routine nursing assessments and other relevant information (e.g. feeding, pharmacological dosing) will be typed and time stamped along with the physiological data stream. Movement will also be digitally recorded independent of the full-acquisition system using wireless actigraphy sensor. All signals, video images and germane data (e.g., medical histories) will be stored on encrypted, password protected computers. Investigators will also manually record relevant study information (timing and mode of experimental conditions, nursing assessments, feeds, medications etc) on log sheets. A log (computer or pen and paper) of the infant's/child's daily activities and nursing interventions will also be obtained, along with relevant clinical information (feeds, withdrawal scores, medications) obtained from electronic medical record for the study session day

NCT03881553 Study Protocol and Statistical Analysis Plan

and up to one day preceding and following each study session.

Study Sessions. The study will be conducted in the UMass Memorial NICU/CCN and in the UMass Memorial Children's Medical Center PICU/PIU. The subject will be studied in the unit in which he/she is receiving care. Enrollment in this study allows the subject to participate in up to 4 full-recording study sessions throughout their hospitalization. A full-recording study session will typically last approximately 8-12 hours (~8am-6pm or ~8pm-6am); some sessions may start earlier/later or go shorter/longer and in some instances we may study the subject for 24 hours (based on research personnel and equipment availability). The reasoning behind a shorter session and for having morning and evening start times is that as the subject matures, s/he may have 'wakeful' periods that prevent study in the crib/bed for certain periods throughout the day. The reasoning behind a 24-hr period is if we have available research-personnel support, we may study a subject throughout a complete 24-hr period to obtain diurnal responses. The number of full-recording sessions the subject participates will depend on duration of hospitalization (e.g., some subjects may be in the hospital longer than others, which will allow more opportunity to participate in multiple study sessions), on availability of research equipment and research personnel, and parent/guardian schedule (e.g., parent/guardian may prefer we not study the subject on certain days, for example if they want to spend time holding the subject or have visitors throughout the day). We will review the infant's/child's medical records and we will obtain additional history through questionnaire from the consenting parent/guardian. We will also obtain medical history on the subject's biological mother, including questionnaire and review of maternal medical records, if available through the UMass Memorial Healthcare system.

Sessions will begin during the infant's/child's feeding, assessment or wake period, during which time sensors for the full-physiology/polysomnography recording will be applied by research study staff; sessions may begin any time if recordings are obtained directly from the bedside monitor. Periods of no intervention (NEATCap device OFF or SVS Mattress OFF) will be alternated with periods of intervention on (NEATCap device ON or SVS Mattress ON). The duration of each intervention period will conform to the routine care of the study subject. Because feeds vary as a function of subject's age, for example premature infants are typically on a fixed ~every 3-4 hours, whereas older infants and children may feed ad-libitum (i.e., as the child desires), the duration of intervention ON and OFF will vary within and between sessions and among subjects. The hospital standard of care for an individual subject, and the subject's sleep/wake cycle will determine the duration of the intervention periods. For subjects who may sleep throughout the night, periods of intervention will conform to either a routine assessment or medication interval (typically ~ every 3-4 hours) to allow for comparisons between intervention ON and intervention OFF with minimal disruption to the subject. The OFF-ON alternating cycles allow subjects to serve as their own control and ascertain if intervention ON leads to consistent, positive responses in the same subject, and assess whether the effect changes over the period.

NEATCap Intervention: At feed/assessment/wake period preceding a

NCT03881553 Study Protocol and Statistical Analysis Plan

NEATCap ON period, the NEATCap device will be fitted and placed on the child by research study staff. The NEATCap device will be removed (OFF) and replaced (ON) at alternating intervals throughout the study session. Physiological data will be recorded throughout the session while the subject is in the crib/bed or hospital-issued sleeping environment (e.g., motorized seat).

SVS Mattress Intervention: At the start of the study session (during a feed/nursing intervention/wake period), the subject's hospital mattress will be replaced or covered with the SVS mattress. For bedside studies in babies cared for in infant crib-warmers that have low guard walls, SVS mattress bedframe extenders (Cofab Design, LLC) will be attached to the guard walls of the infant crib-warmers for the duration of the study session. These bedframe extenders will extend the guard wall 2 inches, the height difference between the SVS mattress and the standard crib-warmer mattress. The study staff will turn the external mattress controller off (SVS Mattress OFF) and on (SVS Mattress ON) at alternating periods throughout the study session. Physiological data will be recorded throughout the session while the subject is in the crib/bed with the SVS mattress.

- *Data to be Collected*: Infant/Child subject and biological maternal medical histories including maternal drug use during pregnancy (if applicable), infant/child daily clinical care measurements (feeds, medications, withdrawal scores), and analyzed data (i.e., scored sleep studies; actigraph and physiological data) comprise the data obtained from subjects. Data may be obtained directly from infant/child medical record, maternal medical record, and/or questionnaire administered to person/s providing informed consent. All data will be collected solely for the proposed research studies.
- *Medical record review*: Subject's medical records will be reviewed and additional history will be obtained from parent/guardian, including review of biological mother medical records if in the UMass Memorial medical record system. We may review medical records throughout the infant's/child's hospitalization and for up to 1-year post hospital discharge. Study staff may review medical records for information pertinent to this study enrollment period until the study is closed out. We request protected health information from general medical records and review of statutorily protected records at this institution to: 1) Make sure the infant/child meets inclusion criteria; 2) Obtain toxicology reports indicating drugs of exposure and other relevant records pertaining to NAS and/or iatrogenic drug withdrawal; 3) Obtain information about factors that may influence the physiological function of the infant/child (e.g., prenatal and postnatal care and prenatal drug exposures; critical-care illness for which the child is being treated in the NICU/PICU, and post-discharge followup). We request to review both the infant's/child's and mother's medical records for information from cardiac studies, nursing and respiratory therapy notes, clinical monitor information, intake and discharge summaries, daily assessments (feeds, medications, withdrawal scores), EEG/EMG studies, laboratory results, operative procedures, conclusive pathologies, clinical problem

NCT03881553 Study Protocol and Statistical Analysis Plan

list, and pulmonary, radiology and rehabilitation information. Data collected will be stored on REDCap forms.

- ***Covid-19 Related Procedures:***

In accordance Joint UMCCTS_IRB Covid-19 Guidance v2 031720, we restricted human subjects-related research as follows:

1. Halted enrollment
2. Halted all in-person bedside studies

As per IRB and CCTS Guidelines and Job aid for reopening human subjects' research during the Covid-19 pandemic, the following procedures will be employed upon IRB approval to resume in-person research studies to help ensure the safety of study participants and their families, research staff, and personnel involved in the care of the infant throughout study enrollment.

Research study staff will comply with ongoing Institutional Covid-19 requirements and adhere to unit safety precautions.

Approval has been obtained from study safety officers and medical caregivers in clinical departments to resume studies in infants' respective units where the bedside studies are conducted with the following procedures:

1. **Recruitment:** We will continue to identify subjects through medical record (HIPAA waiver in place) and obtain approval from subject's medical caregiver within the subject's unit department for approaching candidates who meet criteria. Any known COVID-19 positive patients will be excluded from study.
2. **Consent of new study subjects:** Given that infant-subjects are in-hospital at time of consent, in-person consents will be obtained via current process with the following additional Institutional recommended Covid-19 safety measures by research staff: e.g., social distancing, masks, hand-washing. Writing pens will be wiped with Institutional-hospital cleaning/sterilizing wipes before and after obtaining each hard-copy signature. Remote consenting procedures as per Job Aide for reopening humans subjects' research guidelines may be used in instances when study staff is unavailable to consent in person (e.g., Due to Covid-19 Institutional restrictions on number of personnel allowed in office on a given workday, research personnel with consenting privileges may not be on site at a time conducive to obtaining timely consents). Verbal informed consents in hospital may be conducted via electronic video-chat/zoom/call, and may be obtained from subject by research staff within the consenting time frame. Hard-copy signatures will be obtained from the subject and researcher obtaining consent, or by another researcher with consenting privileges who subsequently reviews the consent with the subject in person prior to start of any intervention.
3. **Bedside Studies:** We will follow Institutional unit Covid-19 safety protocol for cleaning/sanitizing bedside study equipment, devices, and sensors that are not disposable (e.g., mattress, study cables, bedside laptops, ipads, actigraph, pens). We will abide by all unit safety precautions for infant and adult participants, including caregivers who have in-patient privileges with the in-patient infant. For adult subjects/caregivers who are in hospital and participating

NCT03881553 Study Protocol and Statistical Analysis Plan

in study questionnaires on behalf of themselves and/or their infant at the bedside, research staff will comply with all unit safety requirements. Questionnaire testing materials (e.g., pens, ipads, clip boards) will be cleaned before and after use with hospital sanitizing wipes. Adult subjects will wear gloves while completing paper/electronic questionnaires. Research staff will comply with unit safety measures, e.g. mask, gown and glove, during bedside sessions, in addition to routine hand washing and hand sanitizing.

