6. DATA ANALYSIS AND MANAGEMENT*

Statistical Procedures and Power Analysis.

Study design will allow systematic quantification (mean and variance) of the effects of NEATCap device and SVS mattress on automatic function, such as breathing (IBI), cardiac rhythm (R-R), frequency and duration of body movements (e.g., defined via streamlined video, artifact in pulse-oximeter plethysmographic activity, and actigraph count), blood oxygenation (e.g., durations<85%), skin temperature, and sleep states. Analyses will be conducted to determine whether interventions impinge on neural oscillators that drive breathing and cardiac control, and whether NEATCap device reduces dangerous levels of environmental noise, to improve autonomic function and sleep activity.

NCT03881553 Study Protocol and Statistical Analysis Plan

Signal processing algorithms will be used to characterize separately the instability of physiological signals, such as respiration and heartbeat. We will explore, for example, whether different durations of movement periods (e.g., 1.5-5 sec; >5 sec; >10sec) have unique relationships with withdrawal (NAS or iatrogenic) or prematurity, and are affected differently with different interventions (NEATCap device and SVS Mattress).

Parametric tests will be used for analyses of all continuous variables. The Friedman's and Wilcoxon signed-rank tests will be used for nonparametric analyses. For analyses of parametric data separate repeated measures ANOVAs will test effects of stimulus condition (ON or OFF) and trial order. Post-hoc pairwise t-tests will determine differences in responses for conditions of stimulation ON and OFF. For example, separate repeated measures ANOVAs will test effects of stimulus condition (ON or OFF) and trial order on physiological variables. Time of intervention (e.g., infant age, severity of NAS) will be a covariate to assess whether there are critical periods in infant development for optimizing the intervention as a therapeutic strategy. Pearson product-moment correlation coefficient analysis will be used to establish associations between breathing stability (IBI variance) and movement duration, with the expectation that greater variance in respiratory parameters will be positively correlated with excessive movement. *P* values of <0.05 will be considered significant.

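### The Randomization paragraph contains no random element and leaves the starting condition open, so a common start would confound the ON/OFF effect with time in session

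*Combined protocol and SAP*

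**What the plan says.** In Section 4 (Procedures Involved), the paragraph labelled Randomization ties the number and content of sessions to length of stay, staff, device availability and device fit. It then states: "Subject will serve as his/her own control, and will receive alternating periods of intervention ON vs intervention OFF". It describes no list, random allocation or counterbalancing. Section 6 adds that the intervention for a session depends on the availability of equipment and personnel.

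The starting condition is never stated, and the wording points both ways:

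- Study Sessions: "The OFF-ON alternating cycles allow subjects to serve as their own control", which leans towards OFF first.
- SVS mattress: "The study staff will turn the external mattress controller off (SVS Mattress OFF) and on (SVS Mattress ON) at alternating periods", which also names off before on.
- NEATCap: "The NEATCap device will be removed (OFF) and replaced (ON) at alternating intervals throughout the study session", which could be read as ON first.

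Sessions begin at a feed, assessment or wake period, "during which time sensors for the full-physiology/polysomnography recording will be applied by research study staff". Sessions recorded directly from the bedside monitor may begin at any time. Sessions typically last about 8 to 12 hours, by day or by night, though "some sessions may start earlier/later or go shorter/longer" and a few may run to 24 hours. Where periods follow assessments or medication they last about 3 to 4 hours.

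Section 6 (Data Analysis and Management) plans that "separate repeated measures ANOVAs will test effects of stimulus condition (ON or OFF) and trial order", without defining trial order. It adds: "Post-hoc pairwise t-tests will determine differences in responses for conditions of stimulation ON and OFF".

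**The concern.** The contrast between ON and OFF within a child is the core comparison of the study. Using each child as its own control removes differences between children. It does not remove anything that changes over the session in the same way for most children. With strict alternation from a common start, the ON periods sit at fixed positions, so such a change can be read as a device effect or can hide one.

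The clearest candidate is settling after sensors are applied at the start, because movement, breathing, heart rate and sleep are the outcomes. Clock time and the care cycle are not claimed as sources: sessions start by day or by night, and both conditions follow the care cycle.

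**Working it through.** The documents give no sample size, power or effect size, so there is no figure of the plan to reproduce. The check has three parts.

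**1. Periods per session.** From Section 4, 8 h / 4 h = 2, 12 h / 4 h = 3, 12 h / 3 h = 4, 24 h / 4 h = 6 and 24 h / 3 h = 8. Assume session length uniform on 8–12 h and period length uniform on 3–4 h. Counting complete periods only, the share with two periods is the mean of (3D − 8)/4 over period length D, which is (10.5 − 8)/4 = 62.5%. The other 37.5% have three (63/37 is used below). Rounding to the nearest whole number instead gives 20% two, 72% three and 8% four.

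**2. How ON lines up with time.** Equal periods, OFF first; ON first only reverses the signs.

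| Periods | Mean ON position minus mean OFF position | Correlation of ON with linear time | With quadratic time |
|---|---|---|---|
| 2 | 1 | 1.00 | – |
| 3 | 0 | 0 | −1.00 |
| 4 | 1 | 0.45 | 0 |
| 6 | 1 | 0.29 | 0 |
| 8 | 1 | 0.22 | 0 |

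With an even number of periods, the unadjusted ON minus OFF mean absorbs one full period of linear drift. With three, linear drift cancels but curvature is wholly confounded. With equal numbers of each start, the position gap and the linear correlation are 0 for every count from 2 to 8.

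What the undefined trial order term can do under a common start:

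- *Period position as a category:* aliased with condition. The design matrix is one short of full rank for every count from 2 to 8 (for mixed two- and three-period sessions with child effects, rank 32 of 33 columns). With both starts it is full rank.
- *Cycle number:* drift within a cycle stays in the ON effect. At four periods the ON coefficient equals 1.0 times the drift per period.
- *Linear term:* not separable from condition in two-period sessions, and it removes only linear drift in longer ones. A first-period shift s is reproduced exactly, at two or three periods, by a slope of −s/2 and an ON effect of −s/2. For s = 0.5 SD the bias is −0.25 SD.
- *Starting sequence:* has one level, so it adjusts for nothing.

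**3. Illustrative size.** Assumptions not in the documents: 30 children, one session each, within-child period SD 1, no true effect, all OFF-first, two-sided 5% paired t-test on each child's mean ON minus mean OFF (40,000 simulated runs). Under the 63/37 mix the mean bias is 0.63b for drift b per period (0.315 SD at b = 0.5). For a first-period shift s it is 0.63s + 0.37s/2 = 0.815s (0.41 SD at s = 0.5).

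| Session mix | Drift 0.3 | Drift 0.5 | Shift 0.5 |
|---|---|---|---|
| 63% two, 37% three | 11.1% | 23.0% | 35.8% |
| All two | 20.6% | 46.7% | 46.7% (same as drift) |
| All three | 5% | 5% | 19.0% |
| 20% two, 72% three, 8% four | 6.5% | 9.1% | 24.7% |

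Under the 63/37 mix, a drift of 0.1 gives 5.7% and a shift of 0.3 gives 16.0%. Drift of 0.5 gives 16.3% with 20 children and 29.3% with 40. A random start gives 4.8–5.3% throughout.

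In a model with child effects (19 two-period and 11 three-period sessions), OFF-first with a linear term and a 0.5 SD shift rejects in 15.1% of runs. Both starts with categorical period gives no bias and 5.1%.

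**The case against.** The strongest reply is that confounding requires a shared start, which no passage asserts. If both starts occur in practice, even unrandomised, the aliasing is broken or reduced. Trial order could mean ON-first versus OFF-first, which would suggest that the authors expect varied starts, and the t-tests are described as post hoc to an ANOVA that already includes order. Repeated alternation, up to four sessions and variable period lengths give some protection.

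The error rates also depend on assumed drift, sample size and rounding: drift of 0.5 gives 23.0% under one counting rule and 9.1% under the other. A 0.5 SD shift in a whole period mean is demanding. If settling lasted one hour of a 3 to 4 hour period, that hour would need a disturbance of 1.5 to 2 SD. Later periods also follow handling, and sessions recorded from the bedside monitor may avoid sensor settling. Finally, OFF-first is defensible because it limits carryover.

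Much of this stands. The size of any bias is unknown, and the percentages only illustrate it. But the sequence reading of trial order itself needs both starts, which the plan does not secure. Starts left to bedside choice are not randomised. Variable lengths and day or night starts loosen the link with elapsed and clock time, but not with position in the session.

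**Conclusion.** The concern holds. The plan neither randomises nor fixes the starting condition, and the planned analysis cannot be relied on to separate device from time unless both starts occur. Confidence in that gap is high. Actual bias depends on sessions sharing a start, towards which the wording leans without requiring it, and on a time effect within the session.

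Under the stated assumptions, unadjusted false-positive rates run from close to the nominal 5% (small drift, or linear drift with three equal periods) to 47% (drift of 0.5 SD, all two-period sessions). Settling is the more persistent problem: a 0.5 SD first-period shift gives 19% to 47% across the session mixes examined, and a linear time term leaves half of the shift as bias. This should be fixed, because it affects the interpretation of the main contrast and the remedy is cheap.

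**What to change.** Randomise the starting condition of each session, ON-first or OFF-first, from a pre-generated list. Balance it within child where there are several sessions, and by day or night start, then keep the alternation. State this in the Randomization, Study Sessions and device paragraphs of Section 4. In Section 6, define trial order as period position, include it in the ON/OFF model, and base the comparison on that model rather than on unadjusted t-tests. Report the contrast by starting order as a carryover check, relying on sessions with three or more periods; with two, carryover cannot be separated from a period effect. Describe the exploratory comparison between devices as non-randomised, since devices are assigned by availability.

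The cost is a protocol sentence, a list and a line in the analysis plan, with no extra visits, staff or patients. There are two drawbacks. In ON-first NEATCap sessions the cap is fitted during sensor set-up. Carryover also reaches more OFF periods: if a share c of the effect persists for one period, the average contrast is diluted by 0.63 × 0.5c + 0.37 × 0.75c = 0.59c with a random start, against 0.37 × 0.5c = 0.19c with OFF-first (63/37 mix). That shrinks a true effect but creates no false positive when there is none. Exact balance within child is impossible for children with one session; there the list balances across children.

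### In NEATCap sessions recorded with EEG, the cap is worn in ON periods only and handled with head electrodes attached, so sleep scoring may differ by condition without any effect on sleep

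*Combined protocol and SAP*

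**What the plan says.** All of this is in the combined protocol and SAP.

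- **The device (Section 4, Devices).** The NEATCap is "comprised of a soft fabric headband with a specially-designed ear covering". Section 4 opens by making session participation depend in part on "fit-ability of the device around the head and ears of the subject".
- **The measurement (Section 4, Standard measurements and recordings).** "Electrodes over the head and face area will be used to measure EEG activity at the surface of the cortex", and the purpose is "to allow for sleep stage classification using EEG signal analysis". The same sentence ends with a safeguard: "electrode impedance will be measured to help ensure data quality". Not every recording has EEG: "Physiologic recordings with and without electroencephalographic (EEG) activity will be obtained".
- **The sequence (Section 4, Study Sessions and NEATCap Intervention).** Sessions with full recording begin in a feeding, assessment or wake period, "during which time sensors for the full-physiology/polysomnography recording will be applied by research study staff". After that, "The NEATCap device will be removed (OFF) and replaced (ON) at alternating intervals throughout the study session". No inactive cap is described for OFF. The SVS mattress differs: it stays in place and only its controller is switched.
- **The analysis (Section 6).** Sleep states are among the listed outcomes, and promoting sleep is one of the effects to be tested. ON and OFF are compared by repeated measures ANOVA with condition and trial order as factors. Section 6 has no rule for artefact or rejected epochs and no comparison of usable EEG between conditions.

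**The concern.** The cap and the EEG sensors share the head, and the cap is there in one condition only. If it presses on electrodes or leads, or adds movement artefact, some ON epochs may become unscorable or be scored to the wrong state. The ON-OFF contrast in sleep would then contain a measurement difference as well as any effect of the cap.

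Using each child as his or her own control does not remove this, because the artefact would follow the very contrast being tested. More children or more periods would not remove it either; they would only estimate the mixture more precisely. At stake is whether a NEATCap sleep result, in either direction, can be read as an effect on sleep.

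**Working it through.** The plan states no figure on EEG quality, scorable time or expected sleep share, so there is nothing to reproduce. The check has two parts.

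**1. The chain of facts**

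- Electrodes go on at the start of a full-recording session and the cap is exchanged through the session. The exchanges therefore happen with electrodes in place.
- Wearing the cap is confined to ON. Disturbance is not: taking the cap off can shift a lead at the start of the OFF period, and a shifted lead can stay shifted.
- The impedance sentence gives no timing, no threshold and no repeat after a cap change. A reading at session start would miss a later displacement, and impedance alone would not show movement artefact.
- The ANOVA terms are condition and trial order. Neither separates a condition-linked artefact from a sleep effect.

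**2. Size, on assumed inputs**

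None of these values is in the documents:

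- true sleep share p = 0.70 in both conditions, so the true difference is 0;
- unscorable share u = 0.10 in ON and 0.03 in OFF;
- w = share of unscorable epochs that are truly wake, varied.

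If unscorable epochs are dropped, apparent sleep = [p - u(1 - w)] / (1 - u).

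| w | ON | OFF | ON - OFF |
|---|---|---|---|
| 0.30 (loss unrelated to state) | 0.63/0.90 = 70.0% | 0.679/0.97 = 70.0% | 0 |
| 0.70 | 0.67/0.90 = 74.44% | 0.691/0.97 = 71.24% | +3.2 points |
| 0.80 | 0.68/0.90 = 75.56% | 0.694/0.97 = 71.55% | +4.0 points |
| 1.00 | 0.70/0.90 = 77.8% | 0.70/0.97 = 72.2% | +5.6 points |

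Below w = 0.30 the sign turns negative. In the extreme w = 0: 0.60/0.90 = 66.7% against 0.67/0.97 = 69.1%, or -2.4 points.

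If the same epochs are kept and scored as wake, apparent sleep = p - u(1 - w).

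- w = 1.00: 70.0% and 70.0%, difference 0.
- w = 0.80: 68.0% and 69.4%, difference -1.4 points.
- w = 0.30: 63.0% and 67.9%, difference -4.9 points.

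**What bounding would show.** Take w = 0.80. With unscorable epochs counted as wake in both conditions, the difference is 68.0 - 69.4 = -1.4 points. With them counted as sleep in both, it is (68.0 + 10.0) - (69.4 + 3.0) = 78.0 - 72.4 = +5.6 points. The interval contains the true value of 0, whereas simply dropping the epochs reports +4.0.

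**The case against.** The strongest reply is that this is a risk built on an inference.

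- **No electrode sites are given.** A reader might infer that the band sits on the electrodes and presses them. The documents say only that both are on the head. The Devices paragraph also points to a section 32 that is not in the public document, so a montage or scoring procedure elsewhere can be neither confirmed nor excluded. This stands: contact is possible, not shown.
- **Disturbance is not confined to ON.** This also stands. Part of it would follow trial order, which the ANOVA includes. The part that comes from wearing the cap would still follow condition.
- **There are safeguards.** Impedance is measured, and staff fit the cap in a care or wake period when a loose lead could be noticed. Synchronised video, the pulse signal and actigraphy give evidence on movement that does not depend on the head sensors. These help, but the plan does not tie impedance to the cap changes or say that the other signals will be used to judge EEG epochs.
- **The size is assumed.** A reader might take 5.6 points as the expected bias. It is the figure for the case in which every lost epoch is wake, and the bias can be zero. Nor does scoring artefact as wake automatically reverse the bias: if those epochs are all truly wake, that scoring is correct and the difference is 0. A reversal needs some of them to be sleep.
- **The scope is narrow.** Breathing, ECG, oximetry and limb actigraphy use sensors away from the head. No outcome is ranked, so sleep cannot be called the main NEATCap outcome, though it is a stated aim.

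**Conclusion.** The point holds as an uncontrolled measurement risk in NEATCap sessions that include EEG, and only there. It rests on three facts in the plan: the cap is worn on the head in ON only, sleep is staged from head and face electrodes already attached when the cap is exchanged, and no stated step would reveal a difference in EEG quality between conditions.

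The documents do not show that EEG quality does differ, in which direction, or by how much. With true sleep of 70% and unscorable shares of 10% and 3%, dropping epochs gives a spurious difference of 0 to +5.6 points when lost epochs are at least as often wake as epochs in general. Scoring them as wake gives -1.4 points when 20% of them are truly sleep. All of these sizes depend on the assumed inputs. The point deserves a change because the plan as written cannot tell these cases apart and the remedy is small.

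**What to change.** For NEATCap sessions recorded with EEG, add to Sections 4 and 6:

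1. Take the impedance reading after each cap placement and each removal, and log it with the condition times that staff already record.
2. Score ON and OFF from the same derivations within a session.
3. Report the number and share of unscorable epochs by condition.
4. Present the ON-OFF sleep result with unscorable epochs counted as all wake and as all sleep, beside the result with them dropped.

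Exclude electrodes from scoring only if the montage shows that the cap covers them. A blanket exclusion would give up channels for an overlap that is not established.

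The cost is a short impedance check at each switch and a little more analysis. Nothing in the care of the child changes.
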